S2/S3 - Patients with severity of UC classified as "S2 - Moderate UC (passage of more than four stools per day but with minimal signs of systemic toxicity)" or "S3 - Severe UC (passage of at least 6 bloody stools daily, pulse rate of at least 90 beats per minute, temperature of at least 37,5°C, hemoglobin of less than 10,5 g/100ml, and ESR of at least 30mm/h)".

**IBDQ score and IBDQ domains** at Day 1 - The following formulas must be considered:

$$Bowel systems = \frac{Sum of scores: Questions 01, 05, 09, 13, 17, 20, 22, 24, 26 and 29}{10}$$

$$Emotional health = \frac{Sum of scores: Questions 03, 07, 11, 15, 19, 21, 23, 25, 27, 30, 31 and 32}{12}$$

$$Systematic systems = \frac{Sum of scores: Questions 02, 06, 10, 14 and 18}{5}$$

$$Social function = \frac{Sum of scores: Questions 04, 08, 12, 16 and 28}{5}$$

$$IBDQ \ score = Sum of \ all \ scores \ of \ all \ questions$$

Protocol IBD-5004 RISE AR

rerms of Use

**WPAI Questionnaire (for Crohn's Disease and Ulcerative Colitis)** at Day 1 - The following formulas must be considered:

TWPI (Absenteeism and Presenteeism combined)

$$= \frac{Q2}{(Q2+Q4)} + \left[1 - \left(\frac{Q2}{Q2+Q4}\right) \times \frac{Q5}{10}\right] \times 100$$

Percent work time missed due to IBD (Absenteeism) =  $\frac{Q2}{(Q2+Q4)} \times 100$ 

Percent impairment while working due to IBD (Presenteeism) =  $\frac{Q5}{10} \times 100^{\circ}$ 

Percent total activity impairment due to  $IBD = \frac{Q6}{10} \times 100$ 

Absenteeism due to Crohn's disease/Ulcerative Colitis - A dichotomous variable (yes/no) will be calculated:

Yes – Patients with percent work time missed due to IBD (absenteeism) higher than 0%.

No – Patients with percent work time missed due to IBD (absenteeism) equal to 0%.

Work impairment due to Crohn's disease/Ulcerative Colitis - A dichotomous variable (yes/no) will be calculated:

Yes – Patients with percent impairment while working due to IBD (presenteeism) higher than 0%.

No – Patients with percent impairment while working due to IBD (presenteeism) equal to 0%.

Activity impairment due to Crohn's disease/Ulcerative Colitis - A dichotomous variable (yes/no) will be calculated:

Yes – Patients with percent total activity impairment due to IBD higher than 0%.

No – Patients with percent total activity impairment due to IBD equal to 0%.

**Total number of surgeries per patient** – Sum of all previous surgeries due to IBD realized by each patient in the previous 3 years.

is of Use

**Total number of hospitalizations per patient** – Sum of all previous hospitalizations due to IBD for each patient in the previous 3 years.

**Time of hospitalization** – The difference between the start date and end date of each hospitalization, in days. For each patient all hospitalized time will be summed. Time of hospitalization will only be calculated if start date and end date of hospitalization is complete.

**Total number of medical appointments per patient –** Sum of all previous medical appointments for IBD by each patient in the previous 3 years.

Any change in IBD treatment during medical appointments in the previous 3 years per patient – A dichotomous variable (yes/no) will be calculated:

Yes – Patients with at least one medical decision regarding any IBD classes classified as: Introduced a new therapeutic class, Discontinuation (no switch), Drug change (same therapeutic class) or Switched of therapeutic class or Dose changed (same drug).

No – Patients without medical decisions regarding any IBD classes classified as: Introduced a new therapeutic class, Discontinuation (no switch), Drug change (same therapeutic class), Switched of therapeutic class or Dose changed (same drug).

Total number of IBD treatment changes per patient during medical appointments in the previous 3 years – Sum of all medical decisions classified as Introduced a new therapeutic class, Discontinuation (no switch), Drug change (same therapeutic class), Switched of therapeutic class or Dose changed (same drug) for all medical appointments and any IBD classes, in the previous 3 years, for each patient.

**Height (in the previous 3 years, not considering Day 1)** – For each patient, height in the previous 3 years will be calculated by the mean of all heights collected in that period.

Weight (in the previous 3 years, not considering Day 1) – For each patient, weight in the previous 3 years will be calculated by the mean of all weight collected in that period.

IBM (in the previous 3 years, not considering Day 1) - The following formula must be i erms of Use considered:

*IBM* (*in the previous* 3 *years*)

Mean weight in the previous 3 years not considering Day 1 (Kg) Mean height in the previous 3 years , not considering Day 1  $(m)^2$ 

BMI categories (in the previous 3 years, not considering Day 1) - The BMP (in the and subject to the at previous 3 years, not considering Day 1) will be recoded according to the following cut-offs:

Underweight – BMI <18.50 kg/m^2

Normal range – BMI between 18.50 and 24.99 kg/m^2

Overweight – BMI between 25.00 and 29.99 kg/m^2

Obese – BMI  $\geq$  30.00 kg/m^2

Total number of fecal calprotectin levels per patient - For each patient, fecal calprotectin levels in the previous 3 years will be calculated by the mean of all fecal calprotectin levels collected in that period.

Fecal calprotectin results suggestive of inadequate activity control at least one time -A dichotomous variable (yes/no) will be calculated:

Yes – Patients with at least one fecal calprotectin suggestive of inadequate control of activity collected in the previous 3 years.

Patients without fecal calprotectin suggestive of inadequate control of activity collected in the previous 3 years.

Colonoscopy results suggestive of inadequate activity control - A dichotomous variable (yes/no) will be calculated:

Yes – Patients with at least one colonoscopy suggestive of inadequate control of activity collected in the previous 3 years.

No – Patients without colonoscopy suggestive of inadequate control of activity collected in the previous 3 years.

Total number of previous imaging and laboratory testing due to IBD per patient – Sum of all previous imaging and laboratory testing due to IBD for each patient, in the previous 3 years.

**Classes of IBD therapy** – IBD therapies during the previous 3 years will be recoded according to the following categories:

Salicylic derivates: 1.1. sulphassalazine (SSZ), 1.2 Mesalazine (5-ASA), 1.3 Olsalazine and 1.4 Mesalazine extended release.

Corticosteroids: 2.1 Hydrocortisone, 2.2 Prednisone, 2.3 Prednisolone, 2.4 Budenoside and 2.5 Methylprednisolone.

Immunosuppressors: 3.1 Azathioprine, 3.2 6-Mercaptopurine, 3.3 Methotrexate, 3.4 Cyclosporine and 3.5 Tacrolimus.

Biologic therapy: 4.1 Infliximab, 4.2 Adalimumab, 4.3 Vedolizumab, 4.4 Certolizumab, 4.5 Golimumab and 4.6 Ustekimumab.

Antibiotics: 5.1 Metronidazole and 5.2 Ciprofloxacin.

Nutritional support: 6.1 Enteral nutrition and 6.2 Parenteral nutrition.

Others: rest of the IBD therapies.

Frist treatment start/change after moderate to severe IBD diagnosis per patient – A dichotomous variable (yes/no) will be calculated:

Yes – Patients with at least one first treatment start/change after moderate to severe IBD diagnosis.

No – Patients without first treatment start/change after moderate to severe IBD diagnosis or first IBD treatment after moderate to severe IBD diagnosis not applicable.

**First IBD treatment combinations after moderate to severe IBD diagnosis** – First IBD therapies after moderate to severe IBD diagnosis will be recoded according to the following categories

Only salicylic derivates – Patients with only salicylic derivates (sulphassalazine, mesalazine, olsalazine or mesalazine extended release) for IBD first treatment after moderate to severe IBD diagnosis.

Only corticosteroids – Patients with only corticosteroids (hydrocortisone, prednisone, prednisolone, budenoside or methylprednisolone) for IBD first treatment after moderate to severe IBD diagnosis.

Only immunosuppressors – Patients with only immunosuppressors (azathioprine, mercaptopurine, methotrexate, cyclosporine or tacrolimus) for IBD first treatment after moderate to severe IBD diagnosis.

Only biologic therapy – Patients with only biologic therapy (infliximab, adalimumab, vedolizumab, certolizumab, golimumab or ustekimumab for IBD first treatment after moderate to severe IBD diagnosis.

Only antibiotics – Patients with only antibiotics (metronidazole or ciprofloxacin) for IBD first treatment after moderate to severe IBD diagnosis.

Only nutritional support – Patients with only nutritional support (enteral nutrition or parenteral nutrition) for IBD first treatment after moderate to severe IBD diagnosis.

Only other IBD type – Patients with only "other" IBD type for IBD first treatment after moderate to severe IBD diagnosis.

Corticosteroids and antibiotics combination – Patients with corticosteroids and antibiotics combination for IBD first treatment after moderate to severe IBD diagnosis.

Corticosteroids and salicylic derivates combination– Patients with corticosteroids and salicylic derivates combination for IBD first treatment after moderate to severe IBD diagnosis.

Corticosteroids and immunosupressors combination – Patients with corticosteroids and immunosupressors combination for IBD first treatment after moderate to severe IBD diagnosis.

Corticosteroids and biologic therapy combination – Patients with corticosteroids and biologic therapy combination for IBD first treatment after moderate to severe IBD diagnosis.

Immunosupressors and biologic therapy combination – Patients with immunosupressors and biologic therapy combination for IBD first treatment after moderate to severe IBD diagnosis.

Corticosteroids, immunosupressors and biologic therapy – Patients with corticosteroids, immunosupressors and biologic therapy combination for IBD first treatment after moderate to severe IBD diagnosis.

Corticosteroids, immunosupressors and salicylic derivates – Patients with corticosteroids, immunosupressors and salicylic derivates combination for IBD first treatment after moderate to severe IBD diagnosis.

First treatment start/change after moderate to severe IBD diagnosis with only biologic therapy – A dichotomous variable (yes/no) will be calculated.

Only biologic therapy – patients with only biologic therapy treatment in the first IBD treatment after moderate to severe IBD diagnosis.

Other IBD treatments and combinations – patients without biologic therapy treatment or IBD treatment combinations with biologic therapy in the first IBD treatment after moderate to severe IBD diagnosis.

**IBD treatment started/with dose changed at Day 1**– A dichotomous variable (yes/no) will be calculated.

Yes – Patients with at least one IBD treatment (just IBD class of salicylic derivates, corticosteroids, immunosuppressors or biologic therapy) with start date equal to Day 1 date.

No — Patients without any IBD treatment (just IBD class of salicylic derivates, corticosteroids, immunosuppressors or biologic therapy) with start date equal to Day 1 date.

**BD** treatment discontinuation at Day 1– A dichotomous variable (yes/no) will be calculated.

Yes – Patients with at least one IBD treatment (just IBD class of salicylic derivates, corticosteroids, immunosuppressors or biologic therapy) with end date equal to Day 1 date and reason for end of IBD treatment classified as "Discontinued".

SOUSE

No – Patients without any IBD treatment (just IBD class of salicylic derivates, corticosteroids, immunosuppressors or biologic therapy) with end date equal to Day 1 date and reason for end of IBD treatment classified as "Discontinued".

**IBD treatment dose changed at Day 1**– A dichotomous variable (yes/no) will be calculated.

Yes – Patients with at least one IBD treatment (just IBD class of salicylic derivates, corticosteroids, immunosuppressors or biologic therapy) with end date equal to Day 1 date and reason for end of IBD treatment classified as "Dose changed".

No – Patients without any IBD treatment (just IBD class of salicylic derivates, corticosteroids, immunosuppressors or biologic therapy) with end date equal to Day 1 date and reason for end of IBD treatment classified as "Dose changed".

Total number of IBD treatments during retrospective period (previous 3 years and at Day 1) per patient – Sum of IBD treatments reported during retrospective period (3 years) for each patient in the previous 3 years and including IBD treatment starting at Day 1.

**IBD treatment duration** – Time between the beginning of the IBD treatment until the end of the treatment (in months). For patients with ongoing IBD treatment at Day 1, stop date will be considered as Day 1 date visit.

**Salicylic derivates treatment duration per patient** – Sum of all IBD salicylic derivate treatments duration for each patient (in months). If the patient has two IBD salicylic derivate treatments taking in simultaneous, it will only be considered the treatment with the longest duration.

**Corticosteroids treatment duration per patient** – Sum of all IBD corticosteroid treatments duration for each patient (in months). If the patient has two IBD corticosteroids treatments taking in simultaneous, it will only be considered the treatment with the longest duration.

IS OF USE

Immunosuppressors treatment duration per patient - Sum of all IBD immunosuppressor treatments duration for each patient (in months). If the patient has two IBD immunosuppressors treatments taking in simultaneous, it will only be considered the treatment with the longest duration.

Biologic therapy treatment duration per patient - Sum of all IBD biologic therapy treatments duration for each patient (in months). If the patient has two IBD biologic therapies taking in simultaneous, it will only be considered the treatment with the longest duration

Antibiotics treatment duration per patient - Sum of all IBD antibiotic treatments duration for each patient (in months). ,ct to

Nutritional support treatment duration per patient - Sum of all IBD nutritional support snd treatments duration for each patient (in months).

Other treatment duration per patient - Sum of all other IBD treatments duration for each Inmercial USE patient (in months).

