#### 6.3.1 **Inclusion** Criteria

Subjects must meet all of the following inclusion criteria:

- 1) Male or female subjects.
- 2) Subjects aged 18 years or older.
- 3) Diagnosis of moderate to severe CD or UC for at least 6 months prior to Day 1 appointment based on clinical or endoscopic or image criteria (16,17).
- 4) Subjects who provided the written informed consent, onlyanc

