### 5 PROTOCOL CLARIFICATIONS

The last secondary objective, estimation of healthcare resources cost, will not be calculated as stayed in section 3 of the protocol (3. Study objectives), since these variables were not The of Use collected in the CRF.

Adverse events were not collected in the study database and results regarding these variables will not be presented in the statistical report.

Secondary endpoint "Proportion of patients who guit their job due to IBD and have not been able to return to work" will not be calculated as stayed in section 10.1.1 of the protocol (10.1.1 Study endpoints), since these variables were not collected in the CRF

In the protocol the analysis dataset was not defined. In this SAP the analysis dataset was defined according to section 6 Definition of analysis subsets.

The descriptive analysis for continuous variables will be summarized by mean, standard variation, median, maximum, minimum as stayed in the protocol and also by first quartile and third quartile.

## 6

DEFINITION OF ANALYSIS SUBSETS only and Analysis dataset - All patients fulfilling selection criteria (section 4), who provided the written informed consent, without major study protocol deviations and who have completed the Day 1 assessment will be included in the statistical analysis dataset.

### RATIONALE AND CALCULATION OF THE SAMPLE SIZE 7

It is expected to include 246 patients regardless of IBD type.

This sample size will allow estimates with 95% confidence interval and a margin of error less than 5%, and assuming a rate of inadequate control of disease of 20% (conservative approach), regardless of IBD type. The following formula was used:

$$n = \frac{1.96^2 \times p \times (1-p)}{ME^2}$$

Rate of uncontrolled disease (p) = 20%

Margin of error (ME) = 0.05

Expected recruitment period: 6 months

ofUse

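### Three-year totals of IBD-related resource use are shown by disease activity without a companion measure that allows for time since IBD diagnosis

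*SAP*

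**What the plan says.** **Who can enter.** Protocol 6.3.1 requires "Diagnosis of moderate to severe CD or UC for at least 6 months prior to Day 1 appointment". There is no 3-year minimum for this diagnosis or for the first diagnosis of IBD, and the two dates are recorded separately (Protocol 7.2).

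**What is counted.** SAP section 9 defines:
- hospitalizations: "Sum of all previous hospitalizations due to IBD for each patient in the previous 3 years"
- appointments: "Sum of all previous medical appointments for IBD by each patient in the previous 3 years"
- surgeries: "Sum of all previous surgeries due to IBD realized by each patient in the previous 3 years"
- imaging and laboratory tests: a sum of the same form

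Total hospital days and the number of treatment changes are also plain sums.

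**How it is shown.** SAP 8.2 describes these resources by IBD type and by disease activity.

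**What is absent.** SAP sections 8 and 9 give no person-time denominator, rate, restriction to patients with 3 years of disease, or stratification of these counts by disease duration. The one time-scaled resource measure, monthly cost per patient in Protocol 10.3, is dropped in SAP section 5 because the cost variables were not collected. SAP section 9 derives time since IBD diagnosis but does not link it to the counts.

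**The concern.** IBD-related use accrues mainly once a patient has diagnosed IBD. A fixed 3-year sum therefore depends on two things: how intensively the patient used care, and how much of the window fell after diagnosis. When the totals are set side by side for active and not-active disease, a reader will take a difference as a difference in intensity. If the groups differ in time since diagnosis, part or all of that difference could be duration. It could equally hide a real difference in intensity. At stake is the reading of the resource tables by activity, which serve a secondary objective.

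**Working it through.** **The plan's own figure.** The only computed design figure is the sample size in SAP section 7: "It is expected to include 246 patients regardless of IBD type", with p = 0.20 and "Margin of error (ME) = 0.05". The formula gives n = 1.96² × 0.20 × 0.80 / 0.05² = 245.86, rounded up to 246. It reproduces, and nothing below affects it.

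**Inputs from the documents.** The look-back is 36 months (SAP section 3). The minimum time since the moderate to severe diagnosis is 6 months (Protocol 6.3.1).

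**Inputs that are assumed.** The documents do not give the share of patients whose IBD was diagnosed under 3 years ago, how their durations are spread, or event rates. I use shares of 10% to 40%, and either 6 months for every such patient or an even spread over 6 to 36 months (mean 21). The event rate is taken as constant after diagnosis.

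**Step 1: one patient.** Expected total relative to a full-window patient = months since IBD diagnosis / 36.

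| Months since IBD diagnosis | Ratio |
|---|---|
| 6 | 6/36 = 0.17 |
| 12 | 12/36 = 0.33 |
| 18 | 18/36 = 0.50 |
| 24 | 24/36 = 0.67 |
| 36 or more | 1.00 |

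At 1 event per year, the expected totals are 0.5 (6 months) and 3.0 (full window).

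**Step 2: a group mean.** If a share s has t months observed, the group mean relative to full-window patients is (1 − s) + s × t/36.

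| s | t = 6 | t = 21 |
|---|---|---|
| 10% | 0.917 | 0.958 |
| 20% | 0.833 | 0.917 |
| 30% | 0.750 | 0.875 |
| 40% | 0.667 | 0.833 |

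**Step 3: the activity contrast at identical rates.** Suppose 30% of active and 10% of not-active patients have short windows.
- 6 months each: 0.750 / 0.917 = 0.82
- mean 21 months: 0.875 / 0.958 = 0.91

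With the shares reversed, the ratios are 0.917 / 0.750 = 1.22 and 0.958 / 0.875 = 1.10. With equal shares and equal durations the ratio is 1.00. The direction is therefore not known in advance.

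**Step 4: with a denominator.** Dividing events by the smaller of 3 years and time since IBD diagnosis returns 1.00 in every case above, under the constant-rate assumption.

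**The case against.** The strongest reply is that the stated objective is to describe resource use in the 3 years before Day 1, and a 3-year total does exactly that. A patient without diagnosed IBD for part of the window did use fewer IBD resources in it. This stands. A reader might infer that mean resource use is biased downward, but that would hold only if the target were a rate per year of disease, which neither document states.

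Four further points stand in whole or in part:
- **No formal test is named.** A reader might infer that the raw counts will be tested between activity groups. SAP 8.2 only describes them by activity, whereas it names tests for the quality-of-life and WPAI scores.
- **The 6-month minimum concerns the moderate to severe diagnosis.** A reader might infer that anyone recently classed as moderate to severe has a short window. Such a patient may have had milder IBD throughout the 3 years. The 6/36 figure applies only where IBD itself was diagnosed 6 months ago.
- **Use may cluster around diagnosis.** That would shrink or offset the deficit, so the documents do not establish that recently diagnosed patients appear as low users.
- **Duration is not ignored.** SAP 8.2 compares time since diagnosis between activity groups, so an imbalance would be visible. Seeing it does not adjust the counts, and the planned logistic regression models disease control, not resource use.

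A rate also has weaknesses. Diagnostic work-up dated before diagnosis could enter the numerator without matching time in the denominator. SAP section 8 sets a date with missing day and month to 1 July, an error of up to about 6 months, as long as the shortest permitted duration. The fix has to deal with both. Finally, the table shells are an external document (SAP section 10), so a rate shown only there cannot be excluded.

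**Conclusion.** The point holds as a limit on comparability. The raw totals are a valid description of use in the window, but the contrast by activity mixes intensity of use with length of diagnosed disease, and SAP sections 8 and 9 offer nothing to separate them.

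The size depends on shares that the documents do not give. In the assumed 30% versus 10% example, equal rates produce a ratio of 0.82 to 0.91; with balanced durations there is no distortion. These figures also need a constant event rate after diagnosis. If use peaks near diagnosis the gap is smaller or absent, although the totals still rest on unequal observed time.

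The outputs are secondary and descriptive. The primary proportions and the sample size of 246 are unaffected. Label: cheap improvement.

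**What to change.** In SAP sections 8.2 and 9:

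1. Keep the raw 3-year totals as planned.
2. Define observed time as the smaller of 3 years and the time from IBD diagnosis to Day 1. Use the IBD diagnosis date, not the date of the moderate to severe diagnosis.
3. Add events per patient-year of observed time for surgeries, hospitalizations, appointments and tests, by IBD type and activity. Count only events on or after IBD diagnosis in this rate.
4. Add a sensitivity summary in patients with at least 3 years since IBD diagnosis. Every patient there has the full window, so short denominators do not arise, and an imputed diagnosis date matters only near the 3-year boundary.
5. Use a count model (Poisson or negative binomial) with log observed time as offset only if the activity groups are formally tested on these counts.

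The cost is SAP wording, a few table rows and light programming. Diagnosis dates are already collected. Step 3 also needs event dates; the SAP names these for hospitalizations, and I assume the other events are dated, since they must be placed within the window. The downside is that rates are less stable for very short durations, which is why step 4 accompanies step 3.

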# 6.4 Treatments

### 7 Conduct

# 7.1 Data collection overview

Non-interventional study – no treatments/pharmacotherapy are predefined in the protocol.				
All clinical decisions will be full responsibility of the investigator.				
7 Conduct		by are predefined in the protocol. estigator.		
7.1 Data collection overview		icalor.		
Table 1. Study Flow Chart		200		
Study variables	Day 1	Retrospective data Collection data points approximately 3 years		
Timing of data collection	Day 1 visit	During visit		
Informed consent	Х	SUP		
Inclusion criteria	Х			
Exclusion criteria	x	 >		
Socio-demographic variables				
Smoking habits	у SS х			
Anthropometric Information (Weight, Height, BMI)	Х	Х		
IBD type (CD or UC)	Х			
Date of diagnosis of CD or UC (based on medical records)	Х			
Date and criteria of diagnosis of moderate to severe CD or UC (based on medical records)	Х			
Steroid behavior	Х			
Family history of IBD	Х			
Medical history / Comorbidities	Х	Х		
Disease activity: CD (HBI score or CDAI); UC (partial/total Mayo Score)	Х	Х		
Clinical Characterization of Disease: location, behavior, EIM	Х			
SF-36	Х			

Study variables	Day 1	Retrospective data Collection data points approximately 3 years	C.C.
EQ-5D	Х		پ رې ت
IBDQ**	Х		rms of Use
WPAI	Х		
Previous treatments or regimens 	Х	X	
Treatment started at Day 1 (if applicable)	Х	ADIT	
Previous surgeries for IBD		x pilo	
IBD-related hospitalizations		x	
Previous medical appointments related with IBD management			
Previous CDAI, HBI, Mayo score (when available)		x CC	
Previous calprotectin levels and colonoscopy (when available)		d sulla x	
Other previous imaging, laboratory (including PCR) and histology testing (when available)	All'	X	

 Excludes new treatments prescribed at Day 1 visit.

\*\* Not applicable for patients who have a colostomy or ileostomy ercial U

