## 2.1.2 Secondary objectives

- To characterize socio-demographic and clinical aspects of moderate to severe IBD.
- To characterize treatment patterns for IBD during the 3 years previous to Day 1, including the use of biologic therapies and failure to these therapies (if any).

- For each IBD type, to compare patients with moderate to severe disease activity with patients with no or mild activity regarding socio-demographic and clinical variables of interest and treatment patterns.
- ms of Use To evaluate the quality of life (SF-36, EQ-5D and IBDQ) in moderate to severe IBD patients.
- To evaluate the work productivity impairment (WPAI) experienced by moderate to severe IBD patients.
- To describe the use of healthcare resources related with the management of IBD during the 3 years previous to Day 1.
- To estimate UC or CD-related healthcare costs during the 3 years previous to to the app Day 1.

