### **Secondary Analyses** 8.2

The following objectives will be addressed for all IBD patients:

- In order to characterize socio-demographic and clinical aspects of moderate to severe IBD, a summary table with the descriptive statistics of the selected variables, by CD and UC patients.
- Descriptive statistics will also be used to summarize treatment patterns for CD and UC in the previous 3 years, including the use of biologic therapies and failure to these therapies (if any), time between IBD diagnosis and initial treatment, first treatment after diagnosis of moderate to severe IBD, among other variables of interest.
- Within CD and UC groups, the patients with moderate to severe disease activity will be compared with patients with mild or no activity, regarding socio-demographic, clinical and treatment variables of interest:
  - o Chi-square or Fisher exact tests will be used to compare qualitative variables, such as gender, smoking habits, professional status, family history of IBD, steroid behavior (dependent/refractory), previous treatment with biologic therapies, and previous surgery for IBD, among others.
  - The t-student or Mann-Whitney tests will be used for comparison of quantitative variables, such as age, time since diagnosis, and duration of treatment, among others.

 $\infty$  If applicable, logistic regression models (for CD and UC patients) will be used to identify independent variables associated with disease control at Day 1, and odds ratios (OR) with 95% CI will be presented.

For each IBD disease, a descriptive statistical analysis will be used to summarize patients' QoL (Quality of Life), overall and according to disease activity

• The score of EQ-5D analog scale and responses to each item (Mobility, Selfcare, Usual activity, Pain/discomfort, Anxiety/depression):

- Utilities will be configured such that 0 is associated with being dead and 100 is associated with perfect health; thus, a higher utility value is considered better. Mean (SD) utility index will be estimated for CD and UC patients, overall and according to disease activity.

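### The SAP's retrospective treatment count includes treatments started at Day 1, so a comparison of that count by Day 1 activity mixes past treatment with possible reactions to the activity found that day

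*SAP*

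**What the plan says.** The treatment-pattern objective in SAP 2.1.2 is "To characterize treatment patterns for IBD during the 3 years previous to Day 1". In protocol 7.1, Table 1 has a row for previous treatments with the footnote "Excludes new treatments prescribed at Day 1 visit", and a separate row for treatment started at Day 1.

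SAP 9 defines the total number of IBD treatments in the retrospective period as a sum "for each patient in the previous 3 years and including IBD treatment starting at Day 1". The variable's label also mentions Day 1. For treatment duration, SAP 9 adds: "For patients with ongoing IBD treatment at Day 1, stop date will be considered as Day 1 date visit". Treatments started at Day 1 already have a yes/no variable in SAP 9 and an endpoint in SAP 2.2.2.

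SAP 8 and 8.2 compare active with no/mild patients, within CD and within UC, on treatment variables of interest. The quantitative examples are "such as age, time since diagnosis, and duration of treatment, among others". SAP 8 admits variables with p<0.200, or with clinical significance, to the initial logistic model. SAP 5, which lists departures from and clarifications of the protocol, does not mention the count.

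**The concern.** Activity is measured at Day 1, and a drug started at that visit may be a response to it. A variable presented as the 3-year history but containing Day 1 starts therefore partly reflects the outcome it is compared with. Two groups with identical histories would differ on it whenever active patients start treatment at Day 1 more often. A reader would take this as a link between past treatment and present control, and the variable could enter a logistic model as a predictor of control.

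The description also departs from its stated window. Elsewhere SAP 9 takes the opposite line: retrospective height, weight and BMI are defined to leave Day 1 out.

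**Working it through.** **The plan's own figure.** SAP 7: n = 1.96² × 0.20 × 0.80 / 0.05² = 245.86, rounded up to 246. This reproduces, and nothing below changes it.

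**Inputs from the documents.** N = 246; 20% active; two-sided tests at 5%; t-test or Mann-Whitney within each IBD type.

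**Assumptions, because the documents give no figures.**
- Even split of CD and UC: 123 per type, of whom 0.20 × 123 = 24.6, so 25 active and 98 no/mild.
- Identical past counts in both groups, 1 + Poisson(2), mean 3 and variance 2.
- At most one Day 1 start per patient, in 10% of no/mild patients and in 30%, 50% or 70% of active patients.

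**Count.** With equal histories, the expected difference is p_active − p_no/mild: 0.2, 0.4 or 0.6 treatments. The standard error is √[(2 + p_a(1 − p_a))/25 + (2 + p_b(1 − p_b))/98]. For 50% against 10% this is √(2.25/25 + 2.09/98) = √0.1113 = 0.334. So the shift is 0.4/0.334 = 1.20 standard errors, and a 5% test rejects in about 22% of studies. The simulation, with 6,000 runs per setting, agrees:

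| Day 1 starts, active vs no/mild | Spurious difference | Normal approximation | Simulated t-test |
|---|---|---|---|
| none | 0 | 5% | 4.7% |
| 30% vs 10% | 0.2 | 9.3% | 9.4% |
| 50% vs 10% | 0.4 | 22.4% | 23.8% |
| 70% vs 10% | 0.6 | 44.1% | 44.8% |

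Mann-Whitney gives 9.4%, 23.0% and 44.4% in the last three rows. The p<0.200 screen is passed in 28%, 49% and 71% of studies, against 20% without Day 1 starts.

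With past counts of 1 + Poisson(1.5) or 1 + Poisson(3), the three false-positive rates become 7–10%, 18–28% and 30–54%. With equal start rates (10% and 10%) the rate stays near 5%. With Day 1 starts excluded it is 4.1% to 6.2% across settings.

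**Duration per record.** For an ongoing treatment begun at Day 1, start and stop are both Day 1, so the duration is 0 months. With 3 past records averaging 12 months, the mean per record becomes 36/(3 + p): 36/3.5 = 10.3 months at p = 0.5, and 36/3.1 = 11.6 months at p = 0.1.

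**Duration per patient and class.** These variables are sums, and adding 0 changes nothing. Only a patient whose sole record in the class began at Day 1 matters, entering with 0 months. As an illustration, suppose 30% are prior users and 20% of the other 70% start at Day 1. Then 30% + 14% = 44% hold a record in the class, and the mean duration among them falls to 0.30/0.44 = 68% of its true value.

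**The case against.** The inclusion is written out for one variable only, and its label discloses it. The therapy-class recoding in SAP 9 refers to the previous 3 years alone, and Day 1 starts have their own variable and endpoint. A reader might infer that the SAP folds Day 1 treatment into the whole retrospective pattern; the documents do not show that. The protocol footnote qualifies a data-collection row, so the count can be read as an openly labelled sum of two items rather than a redefinition of previous treatments. All of this stands. Disclosure, however, does not remove the mixing of past treatment with reaction, nor make the count match the objective's window.

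The count is also not among the variables that SAP 8.2 names for testing by activity, and the table shells are in an external document. This stands too. The general wording on treatment variables covers the count, but whether it will be tested is not known.

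On duration, a reader might infer that the SAP prescribes zero durations, or that zeros distort every class duration. Neither is supported. The zero follows from the stop-date rule and is not itself stated, and no rule excludes such records. The class variables are sums. For salicylates, corticosteroids, immunosuppressors and biologics, simultaneous treatments are also reduced to the longest.

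Finally, the error rates rest on assumed start rates, and with equal rates there is no inflation. That is correct, and it limits the result to a range.

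**Conclusion.** The concern holds in a limited form. One count labelled retrospective includes Day 1 starts, at odds with the objective's window and the protocol's flow chart. If it is compared by Day 1 activity, it carries a spurious difference equal to the difference in Day 1 start rates. Under the assumptions above (25 against 98, 30–70% against 10%), the false-positive rate is about 9% to 45% instead of 5%. These figures are conditional on the start rates and on the comparison being made; the documents settle neither.

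The effect on duration is an inference and goes the other way: the group with more Day 1 starts appears to have shorter treatments per record. Per-patient class durations change only through patients whose sole record in the class began at Day 1.

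Only secondary treatment-pattern analyses are affected. The primary proportions and N = 246 are not.

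**What to change.** In SAP 9, restrict the retrospective treatment count, the IBD treatment duration and the class-duration variables to treatments with a start date before Day 1. This reconciles the count with protocol Table 1 and the objective.

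Report Day 1 starts only in their existing SAP 9 variable and SAP 2.2.2 endpoint. They may still be described by activity there, since whether active patients were started on treatment is a legitimate question when the result is labelled as Day 1 treatment. Do not offer them to the logistic models as predictors of Day 1 disease control. Check the external table shells for the same point.

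The cost is one date condition in the derivations. No new data are needed: treatment start dates and the Day 1 date are already collected.
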